10.5 Response Duration

Response duration will be measured from the time measurement criteria for CR/PR (whichever is first recorded) are first met until the first date that recurrent or progressive disease is objectively documented, taking as reference the smallest measurements recorded on study (including baseline).

10.6 Stable Disease Duration

Stable disease duration will be measured from the time of start of treatment until the criteria for progression are met, taking as reference the smallest sum on study (including baseline).

10.7 Progression-Free Survival

Progression-free survival (PFS) is defined as the time from study entry until disease progression or death.

10.8 Methods of Measurement for CT-Scan Evaluation

The same method of assessment and the same technique should be used to characterize each identified and reported lesion at baseline and during follow-up as indicated in Section 9. While on study, all lesions recorded at baseline should have their actual measurements recorded at each subsequent evaluation, even when very small (e.g. 2 mm). If it is the opinion of the radiologist that the lesion has likely disappeared, the measurement should be recorded as 0 mm. If the lesion is believed to be present and is faintly seen but too small to measure, a default value of 5 mm should be assigned. For lesions which fragment/split add together the longest diameters of the fragmented portions; for lesions which coalesce, measure the maximal longest diameter for the “merged lesion”.

- 10.8.1 Clinical Lesions. Clinical lesions will only be considered measurable when they are superficial and ≥ 10 mm as assessed using callipers (e.g. skin nodules). For the case of skin lesions, documentation by colour photography including a ruler to estimate the size of the lesion is recommended. If feasible, imaging is preferred. Lymph nodes should be measured by CT scan as described in section 10.2 if followed.
- 10.8.2 Ultrasound. Ultrasound is not useful in assessment of lesion size and should not be used as a method of measurement. If new lesions are identified by ultrasound in the course of the study, confirmation by CT is advised.

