10.2 Documenting Enlarged Lymph Nodes

A maximum of the 6 largest nodes or nodal masses (minimum size $> 1.5 \times 1.5$ cm) will be followed for response if enlarged at baseline. Wherever possible, enlarged nodes should be documented in the nodal disease case report form and followed by CT scan.

Notes:

If a patient does not have baseline lymphocytosis of at least $10 \times 10^9/L$, he or she must have at least one node $\geq 2 \times 2$ cm on CT scan to be eligible.

For additional enlarged lymph nodes/nodal masses beyond the maximum of 6 recorded, record them as “multiple enlarged nodes” as a single entry on the nodal disease case report form. Do not list each individual non-target node or node group as separate lesions.

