Partial Response (PR): To define a PR, at least 1 of the criteria of Group A plus 1 of the criteria of Group B must be met and persist for ≥ 8 weeks, in the absence of any criteria definitive of progressive disease.

Group A:

- A 50% or more decrease in peripheral blood lymphocytes from the value before therapy.
- A 50% or more reduction in lymphadenopathy (by CT scan) either in the sum products of up to 6 measurable lymph nodes, or in the largest diameter of the enlarged lymph node(s) detected prior to therapy.
- A 50% or more reduction in the noted pretreatment enlargement of the spleen or liver, as estimated by CT scan.

Group B:

- The blood count should show one of the following results:
 - Neutrophils more than $1.5 \times 10^9/L$ without need for exogenous growth factors or 50% improvement over baseline without need for exogenous growth factors.
 - Platelet counts greater than $100 \times 10^9/L$ or 50% improvement over baseline without need for exogenous growth factors.

- Hemoglobin greater than 110 g/L or 50% improvement over baseline without requiring red blood cell transfusions or exogenous erythropoietin.

Progressive Disease (PD): Progressive disease during or after therapy is characterized by at least one of the following:

- Progression of lymphadenopathy
 - Appearance of any new lesion, such as new enlarged lymph nodes ($> 1.5 \times 1.5$ cm), splenomegaly, hepatomegaly, or other organ infiltrates.
 - An increase by 50% or more in greatest determined diameter (= greater than 65% increase in bidimensional product) of any previously recorded measurable node.
- An unequivocal increase in the previously noted enlargement of the liver or spleen by an estimated 50% or more or the de novo appearance of hepatomegaly or splenomegaly.
- Transformation to a more aggressive histology (e.g. Richter syndrome).
 - Whenever possible, this diagnosis should be established by lymph node biopsy.
- Occurrence of cytopenia (neutropenia, anemia, or thrombocytopenia) attributable to CLL.
 - During therapy:
 - During therapy, cytopenias cannot be used to define disease progression.
 - After treatment:

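### Section 10.8 measures split and merged nodal masses by diameter only, while Section 10.4 scores response on products, so one entry can meet the progression and partial-response thresholds at the same scan

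*Protocol*

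**What the plan says.** Five provisions of the protocol meet at this point.

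- **What is followed (10.2).** "A maximum of the 6 largest nodes or nodal masses" are tracked, so a matted conglomerate can be a single recorded entry.
- **What is measured (10.8).** At every CT, "all lesions recorded at baseline should have their actual measurements recorded at each subsequent evaluation". For lesions that split or merge, the instruction is "For lesions which fragment/split add together the longest diameters of the fragmented portions; for lesions which coalesce, measure the maximal longest diameter". No product is defined for either case.
- **Nodal partial response (10.4, Group A).** A fall of at least 50% in the sum of products of up to 6 nodes, or in the largest diameter of the enlarged nodes.
- **Nodal progression (10.4).** "An increase by 50% or more in greatest determined diameter (= greater than 65% increase in bidimensional product) of any previously recorded measurable node". One criterion is enough: "Progressive disease during or after therapy is characterized by at least one of the following".
- **How the two interact (10.4).** Partial response must persist for at least 8 weeks "in the absence of any criteria definitive of progressive disease".

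Section 13.1 provides no central radiology review. The SAP plans a waterfall plot of tumour shrinkage, a duration-of-response table and a progression-free survival curve, but adds no measurement rule.

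**The concern.** The split rule works in one dimension. The main nodal response measure works in two. When a mass breaks up, the sum of its fragments' diameters can rise while the sum of their products falls. If the sum from 10.8 is taken as the entry's diameter in the 10.4 progression test, a patient whose nodal disease is shrinking can be called progressive.

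That call overrides every route to partial response, including the lymphocyte-count route, because any progression criterion blocks it. Section 12.2 then takes the patient off study, and Section 10.7 counts the date as a progression-free survival event. In a cohort that continues on 1 response in 5 and rejects the null on 2 in 12, one misread patient can change the conclusion. Without central review, sites may also read the rule differently.

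Merging has the same gap. Section 10.8 gives the merged lesion one diameter but does not say which recorded entry, or combination of entries, it is compared with.

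**Working it through.** **1. The plan's own design (14.2).** Inputs: 5 patients in stage 1, continue with at least 1 response, 12 in total, reject with at least 2 responses, rates 5% and 30%. With X1 ~ Bin(5, p) and X2 ~ Bin(7, p):

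P(reject) = P(X1 ≥ 2) + P(X1 = 1) × P(X2 ≥ 1)

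- p = 0.05: 0.0226 + 0.2036 × 0.3017 = 0.084, within the stated 0.1.
- p = 0.30: 0.4718 + 0.3602 × 0.9176 = 0.802, matching the stated 80%.

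**2. One entry under both measures.** A 6.0 x 4.0 cm mass has product 24.0 cm². It becomes three nodes of 3.0 x 1.2 cm.

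- Summed diameter (10.8): 3 × 3.0 = 9.0 cm; 9.0 / 6.0 = 1.50, or +50%. The diameter threshold for progression is met.
- Summed product: 3 × 3.0 × 1.2 = 10.8 cm²; 10.8 / 24.0 = 0.45, or −55%. The Group A nodal threshold is met.

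**3. When both thresholds are met.** For a mass L x S that splits into k equal fragments a x b, progression on summed diameter needs k·a ≥ 1.5 L, and Group A on summed products needs k·a·b ≤ 0.5 L·S. At exactly k·a = 1.5 L, the second becomes b ≤ S/3. Here S/3 = 1.33 cm and b = 1.2 cm. The outcome therefore depends on shape, as these illustrative splits show:

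| Mass (cm) | Becomes (cm) | Summed diameter | Summed product | Thresholds met |
|---|---|---|---|---|
| 6.0 x 4.0 | three 3.0 x 1.2 | 9.0 (+50%) | 10.8 (−55%) | both |
| 6 x 6 | three 3.2 x 1.8 | 9.6 (+60%) | 17.3 (−52%) | both |
| 6 x 6 | two 4.6 x 1.9 | 9.2 (+53%) | 17.5 (−51%) | both |
| 6 x 6 | two 4 x 2 | 8.0 (+33%) | 16.0 (−56%) | response only |
| 6 x 6 | two 3 x 3 | 6.0 (0%) | 18.0 (−50%) | response only |

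For k equal round fragments of a round mass at exactly +50%, the summed product is 2.25/k of the original: +12.5% for k = 2, −25% for 3, −44% for 4 and −55% for 5. With round pieces, progression and nodal response coincide only from five fragments.

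**4. The product figure in the progression criterion.** A 50% rise in diameter is a 50% rise in product if the other axis is unchanged, and 1.5² − 1 = 125% if both axes grow alike. The stated figure of more than 65% lies between, so the two forms are not equivalent. In step 2 they point in opposite directions: +50% in diameter, −55% in product.

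**5. What is at stake in power.** The documents give no frequency of splitting. Assume a true response rate of 30% and that a share m of responders is lost this way, so that p = 0.30 × (1 − m):

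- m = 5%: power 0.778
- m = 10%: power 0.750
- m = 20%: power 0.688

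**The case against.** The strongest reply is that no sentence identifies the 10.8 sum with the greatest diameter of a node in 10.4. Section 10.8 speaks of lesions in general, 10.8.1 refers lymph nodes to 10.2, and a sum of diameters might have been meant for the largest-diameter route in Group A or for the smallest sum mentioned in 10.6. The progression criterion also carries its own product figure, and a reader who uses it would not call the step 2 example progression. This stands as a limit: the false call depends on the reading. It does not remove the problem. Section 10.2 has no rule for splitting or merging, so nodes fall back on 10.8, and no text says which form of the criterion governs when the two disagree.

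Three stronger readings are tempting, and the documents do not support them.

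- A reader might infer that the summed diameter always exceeds the mass. It does not: 6 x 6 cm into two 3 x 3 cm gives no change.
- A reader might infer a general inflation factor by assuming that nodes fill a mass without gaps. The documents say nothing about packing, and touching spheres in their most compact arrangement give ratios of only 1.5 for three nodes and 2.0 for four. At the +50% limit, three or four round fragments do not reach a 50% fall in product (step 3).
- A reader might infer that merged nodes automatically count as progression against one constituent. Section 10.8 does not instruct that comparison. Measured against the constituents together, the length may have fallen.

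Finally, 10.4 classifies best response, so a partial response already confirmed stands. A later split could still shorten response duration and progression-free survival.

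**Conclusion.** Sections 10.8 and 10.4 do not fit together for nodes that split or merge. Applied literally, they can put one entry past the progression threshold and the nodal response threshold at the same scan, and progression then takes precedence. The primary endpoint is affected only if this happens before the 8-week confirmation.

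The conclusion rests on two conditions: the summed diameter is read as the entry's diameter in the progression test, and the fragments are numerous or thin enough to reach +50%. How often that occurs is unknown, so no expected bias can be given; the power figures show sensitivity to assumed shares only. The point merits a correction because the decision limits are 1 of 5 and 2 of 12, reading is local, and the remedy is small.

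**What to change.** State in 10.8, and on the nodal case report form, that the diameter-sum and merged-diameter rule does not apply to lymph nodes or nodal masses. Then define:

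- **Split nodal mass:** the entry's value is the sum of the fragments' products.
- **Merged nodes:** compare the merged product with the sum of the constituents' smallest recorded products.
- **Use:** apply these values to the Group A 50% reduction and to nodal progression. For progression in such entries, use the increase of more than 65% in product already in 10.4, with the smallest recorded product as reference.

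Do not test progression on the largest fragment alone. A 6.0 x 4.0 cm mass (24 cm²) that becomes three 4.5 x 4.5 cm nodes has a summed product of 60.75 cm² (+153%), yet its largest fragment is 25% shorter than the mass (4.5 against 6.0 cm). That test would miss real growth; the summed product catches it.

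The cost is one paragraph, one form instruction and the short axis of each fragment, read from the existing CT. No extra scan is needed. This concerns endpoint measurement only; how it bears on stopping treatment under 12.2 is for the sponsor to reconcile.

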11.0 SERIOUS ADVERSE EVENT REPORTING

The descriptions and grading scales found in the NCI Common Terminology Criteria for Adverse Events (CTCAE) will be utilized for Adverse Event (AE) reporting (version can be found in Appendix V). All appropriate treatment areas should have access to a copy of the CTCAE. A copy of the CTCAE can be downloaded from the CTEP web site:

http://ctep.cancer.gov/protocolDevelopment/electronic_applications/ctc.htm

All serious adverse events (SAE) defined as per ICH guidelines (see below) and other adverse events must be recorded on case report forms. In addition, all “reportable” serious adverse events are subject to expedited reporting using the CCTG SAE form. The term ‘reportable SAE’ is used in the definitions which follow to describe those SAEs which are subject to expedited reporting to CCTG.

11.1 Definition of a Reportable Serious Adverse Event

- All serious adverse events, regardless of whether they are unexpected or related to protocol treatment, occurring during the treatment period and within 30 days after the last protocol treatment administration, must be reported in an expedited manner. Any late serious adverse event occurring after this 30-day period which is unexpected and related to protocol treatment must also be reported in an expedited manner (see Section 11.2 for reporting instructions).
- A serious adverse event (SAE) is any adverse event that at any dose:
 - results in death
 - is life-threatening
 - requires inpatient hospitalization or prolongation of existing hospitalization (excluding hospital admissions for study drug administration, transfusional support, scheduled elective surgery and admissions for palliative or terminal care)
 - results in persistent or significant disability or incapacity
 - is a congenital anomaly/birth defect

Medical and scientific judgement should be exercised in deciding whether expedited reporting is appropriate in other situations such as important medical events that may not be immediately life-threatening or result in death or hospitalization but may jeopardize the patient or may require intervention to prevent one of the events listed above.

Note: Adverse events which are unequivocally only related to the underlying malignancy or disease progression are NOT reportable Serious Adverse Events. These include such adverse events as admission for pain control, palliative care or paracentesis of malignant effusions.

11.2 Serious Adverse Event Reporting Instructions

All reportable serious adverse events must be reported using a web-based Electronic Data Capture (EDC) system being used for this trial. For details about accessing the EDC system and completing the on-line SAE report form, please refer to the CCTG Generic Data Management Guidebook for EDC Studies posted on the IND. 216 section of the CCTG website (www.ctg.queensu.ca).

AMEND #3: 2016-AUG-24

Within 24 hours: Complete preliminary Serious Adverse Event Report and submit to CCTG via EDC system.

Within 7 days: Update Serious Adverse Event Report as much as possible and submit report to CCTG via EDC system.

EDC SAE web application interruption:

In the rare event that internet connectivity to the EDC SAE system is disrupted, please print and complete a paper copy of the SAE Report, available from the trial specific website.

FAX paper SAE Report to:

[name], Study Coordinator
Canadian Cancer Trials Group
[contact]

Please use the same timelines for submission as for direct EDC reporting.

Once internet connectivity is restored, the information that was FAXED to CCTG on the paper SAE Report must also be entered by the site into the EDC SAE web application.

Local internet interruption:

If you are unable to access the EDC SAE system, and cannot access a paper copy of the SAE Report from the trial website, please phone the IND 216 trial team [contact]) to obtain a copy of the SAE Report by FAX. Once completed, the report must be FAXED back to CCTG as indicated above. Once internet connectivity is restored, the information that was FAXED to CCTG on the paper SAE Report must also be entered by the site into the EDC SAE web application.

In cases of prolonged internet interruptions, please contact the CCTG Safety Desk for further instructions [contact]).

11.3 Other Protocol Reportable Events – Pregnancy/Exposure Reporting

In accordance with CCTG's inclusivity in research policy, women of childbearing potential (WOCBP) may be enrolled in this clinical trial. WOCBP are defined as women who have had a menstrual period during the last year and have not had a hysterectomy. Precautions are required to be taken to prevent pregnancy during the clinical trial when the research population includes WOCBP. This includes pregnancy testing, use of effective methods of birth control, and pregnancy as an exclusion factor. The trial sample informed consent form includes the potential for unidentified risks to the embryo/fetus. It also includes general information on pregnancy prevention and the required minimum period during which birth control must be utilized.

11.3.1 Pregnancy Prevention

WOCBP and males who are enrolled in the trial must be informed of the requirement to use appropriate contraception. Investigators are advised to inform the female partners of male participants when appropriate and compliant with local policy.

AMEND #1: 2015-OCT-22; AMEND #3: 2016-AUG-24

Sexually active males should use a condom during intercourse while taking drug and for 12 weeks after the final dose of study treatment. A condom is required to be used also by vasectomized men in order to prevent delivery of the drug via seminal fluid.

WOCBP must use highly effective contraception while taking drug and for at least 4 weeks after the final dose of study treatment. Highly effective contraception is defined as

- i. total abstinence
- ii. male partner sterilization
- iii. use of a combination of both:
 - a. placement of an intrauterine device (IUD) or intrauterine system (IUS) AND
 - b. barrier methods of contraception: condom or occlusive cap (diaphragm or cervical /vault camps) with spermicidal foam/gel/film/cream/vaginal suppository

Note hormonal contraception methods (oral, injected and implanted) are not allowed as buparlisib decreases the effectiveness of hormonal contraceptives.

11.3.2 Pregnancy Reporting

The investigator is required to report to CCTG any pregnancy occurring in female participants, and female partners of male participants. Pregnancies occurring up to 6 months after the completion of study treatment must also be reported.

The investigator should report the pregnancy in a timely manner, within 24 hours of learning of the pregnancy using the CCTG Pregnancy Reporting Form available from the trial webpage.

Once informed consent has been obtained, the form should be updated to provide further pregnancy information and to reflect the outcome of the pregnancy. All follow-up reports must be submitted to CCTG in a timely manner. For pregnant partner of trial participant (and pregnant participants, if required by local policy), a copy of the signed signature page of the pregnancy follow-up consent must be submitted to CCTG.

Documents outlined above (including updates) must be sent to the CCTG safety desk [contact] / [contact]).

If the pregnancy results in death; is life-threatening; requires inpatient hospitalization or prolongation of existing hospitalization; results in persistent or significant disability/incapacity; is a congenital anomaly/birth defect, then an SAE report must be additionally submitted as described above. Please note, hospitalization for labour/delivery alone does not constitute an 'inpatient hospitalization' for the purposes of pregnancy reporting.

11.3.3 Exposure Reporting (Non-study Participants)

The investigator is required to report to CCTG any incidence of exposure to study agent(s). Exposure is defined as significant, direct, contact/inhalation/consumption of agent(s) by non-study participant (an individual who is not otherwise participating in this clinical trial). An example of an exposure includes a non-study participant swallowing study medication. The investigator is responsible for determining significance, based on the agent to which the individual is exposed.

The investigator should report the exposure in a timely manner, within 24 hours of learning of the exposure, using the CCTG Exposure Reporting Form available from the trial webpage.

Once informed consent has been obtained, the form should be updated to provide further exposure information and to reflect the outcome of the exposure as the information becomes available upon appropriate follow-up of the exposed individual. All follow-up reports must be submitted to CCTG in a timely manner. A copy of the signed exposure follow-up consent signature page must also be submitted to CCTG.

Documents outlined above (including updates) must be sent to the CCTG safety desk [contact] / [contact]).

If the exposure results in death; is life-threatening; requires inpatient hospitalization or prolongation of existing hospitalization; results in persistent or significant disability/incapacity; is a congenital anomaly/birth defect, then an SAE report must be additionally submitted as described above.

11.4 CCTG Responsibility for Reporting Serious Adverse Events to Health Canada

The CCTG will provide expedited reports of SAEs to Health Canada (Office of Clinical Trials) for those events which meet regulatory requirements for expedited reporting, i.e. events which are BOTH serious AND unexpected, AND which are thought to be related to protocol treatment (or for which a causal relationship with protocol treatment cannot be ruled out).

11.5 CCTG Responsibility for Reporting Serious Adverse Events to Novartis

Novartis will be notified of all reportable serious adverse events (SAE) and pregnancies reported as SAEs, within 15 calendar days of receipt.

11.6 Novartis Reporting Responsibilities

Novartis will send all regulatory reportable serious unexpected suspected adverse reactions (SUSARs) from non-CCTG trials (Safety Updates) for buparlisib to CCTG. Novartis will report these events to Health Canada.

